1. STUDY DESIGN

- 1.1. *Study Overview.* This study will use a two-arm randomized study design. Participants will be recruited across three cancer types. Each of the participants will be randomized to an active “intervention” arm (using the full SYNC app) or to a control arm (using a “dummy” version of the SYNC app that gives recommendations for light at times that should not significantly affect the circadian clock). The random allocation of participants to the treatment arm or control arm establishes the basis for testing the statistical significance or difference between the groups in the measured outcome (patient fatigue, assessed by a daily 1-question fatigue survey and the PROMIS 4-item Fatigue). Patient age, gender, and other prognostic baseline characteristics that could potentially confound an observed association, including those that are unknown or unmeasured, will be distributed equally, except through chance alone, through random assignment. Thus, this design is well-suited to our goal of assessing the efficacy of a mobile health intervention, SYNC, on participants.
- 1.2. *Primary Hypothesis.* The primary hypothesis is that a mobile-app delivered circadian intervention (SYNC) will reduce patient fatigue.
- 1.3. *Study Objectives*
 - 1.3.1. Primary Objective. To test the difference between the “intervention” (full SYNC app) arm and the control (limited SYNC app) arm in the measured outcome of patient fatigue, assessed by daily 1 question surveys and weekly 4-item PROMIS questionnaires over the course of 12 weeks.
 - 1.3.2. Secondary Objective. To determine the change in sleep disturbances, anxiety, depression, physical functioning, and global health through PROMIS questionnaires, between baseline and the 12-week assessment in both the control and intervention arms, and to look for differences in this change between the two arms.
 - 1.3.3. Exploratory Objectives
 - 1.3.3.1. Change in patient physical activity through physiological data capture using the wearable sensors in the control versus intervention arm.
 - 1.3.3.2. Change in patient health care utilization (e.g., total count of hospital days, readmissions, and ambulatory care clinic visits) in the control versus intervention arm
 - 1.3.3.3. Change in patient sleep aid usage in the control versus intervention arm.
- 1.4. *Participant Eligibility*
 - 1.4.1. Inclusion Criteria

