- 1.5.4. Participants will be allowed to use sleep aids over the course of the trial. There will be no restriction on their usage; however, subjects will be asked to report on a weekly basis what sleep aids they consumed, as well as the number of alcoholic drinks they consumed. This survey will be carried out in the app.
- 1.5.5. Once the trial has begun, study coordinators will track completion of surveys, and in the event of missing data will follow-up with subjects to assess challenges to encourage survey completion. SYNC software will be maintained in collaboration with Arcascope, Inc. After randomization, subjects will complete baseline assessments, as outlined in the metrics Appendix. They will be asked to wear the wearable device day and night for twelve weeks. During this time, the app will deliver ecological momentary assessments of fatigue daily at random times of day and the validated 4-item PROMIS Fatigue questionnaire weekly to both the control and interventional groups. At the end of the twelve-week period, the subjects will remotely complete end-of-trial assessments.
- 1.5.6. Intervention arm (SYNC app): Participants randomized to the intervention arm will be instructed on how to download the app on their mobile phones (iOS) and how to operate the wearable device. The app will record when the user opens the app, as well as when they check off having completed an assigned task; e.g. “getting bright light exposure”. Please see **Appendix A** to view the components of the wearable device. Please see **Appendix B** to view specifications of the mobile app. Any PHI information will be stored on University of Michigan servers in a secure way. Only non-PHI information will be stored and collected via the Sync app. The SYNC will be downloaded onto patient mobile phones and can be used freely throughout the intervention period because it contains no PHI data.
- 1.5.7. Control arm: Participants randomized to the control arm will be instructed on how to download the SYNC app and how to operate the wearable sensor. Their research ID will trigger the “control” recommendations from SYNC, which are chosen to minimize circadian effect. Any PHI information will be stored on University of Michigan servers in a secure way. Only non-PHI information will be stored and collected via the Sync app. The SYNC will be downloaded onto patient mobile phones and can be used freely throughout the intervention period because it contains no PHI data.

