3. STUDY ENDPOINTS

3.1. *Primary Endpoint.* The primary endpoint is **fatigue**, as assessed by a daily fatigue questionnaire and a weekly 4-item PROMIS fatigue questionnaire.

3.2. *Secondary Endpoint.* The secondary endpoints are sleep disturbance, anxiety, depression, physical function and global health, as measured via the following PROMIS validated instruments:

- PROMIS Sleep Disturbance (8-item)
- PROMIS Anxiety (7-item)
- PROMIS Depression (8-item)
- PROMIS Physical Function (8-item)
- PROMIS Global Health (10-item)

3.3. *Exploratory Endpoints.*

3.3.1. Activity data. Patient activity (steps) and sleep will be measured continuously from the start to the end of the trial through wearable sensors.

3.3.2. Health care utilization data. Patient health care utilization data (e.g., total count of hospital days, emergency department visits, readmissions, and ambulatory care clinic visits) will be captured through the electronic health record as well as self-report (i.e., if the patient is readmitted at an outside hospital other than Michigan Medicine).

3.3.3. Sleep aid utilization data will be collected via self-report in the app once a week.

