5. STATISTICAL CONSIDERATIONS

- 5.1. *Study Design.* The clinical trial is a two-arm randomized controlled trial. After completion of the intervention, data analysis will be conducted according to the statistical analysis plan outlined below. Descriptive statistics will be performed prior to conducting the statistical analyses. An intention-to-treat (ITT) analysis of the results will be based on the initial assignment of the randomized participants. With the ITT approach, participants will be analyzed according to the treatment assignment, even if the participant drops out of the study. The ITT approach minimizes biased comparisons among the treatment arms. Missing data will be imputed using the last collected data from the subject prior to dropout.
- 5.2. *Accrual.* It is estimated that 18-months will be necessary to enroll the targeted sample size. Accrual will be reported by race, ethnicity, gender, and age.
- 5.3. *Study Duration.* Survey results and wearable data will be actively collected from participants over the course of 12 weeks. At the conclusion of the 12 weeks, passive collection of wearable data through the app will continue for up to one year for each participant who opts-in to continue using the app. Medical records may be accessed for up to five years after the conclusion of the 12-week collection period.
- 5.4. *Randomization.* Blocked randomization will be used to limit bias and achieve an equal distribution of participants to the intervention and control arms of the study (69 randomized, 69; with 23 from each cancer population in each arm). This approach will recruit participants in small blocks to ensure that half of the participants within each block will be allocated to the treatment and the other half to the control. The size of the blocks will be permuted to limit selection bias, and within each block, the order of patients will be random. The study statistician will create a randomization list before the study begins enrollment using the statistical package R. This list will be used by the study group in assigning patients to the correct study arm.
- 5.5. *Blinding.* Study arm assignments cannot be blinded to the investigators or the rest of the study team because it will be known whether participants have SYNC on their mobile device or not (due to technical purposes).

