5.14.2. Patient health care utilization. The total count of hospital days, ED visits, readmissions, and ambulatory care clinic visits during the trial, with adjustment for follow-up, will be compared between arms using a Poisson regression model, with adjustment for potential mediating or moderating effects of patient characteristics, if needed. The data will be captured at the time of PRO assessments.

5.14.3. Patient sleep aid utilization. The total number of sleep aids being used by the patients, as well as the types, will be collected via weekly surveys over the course of the trial.

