Sleep aid usage survey

Carrier 5:54 PM Done Weekly

Sleep Aid Usage

If you have used any sleep aids in the past week, select them from the list below:

- Ambien, Ambien CR (zolpidem tartrate)
- Dalmane (flurazepam hydrochloride)
- Halcion (triazolam)
- Lunesta (eszopiclone)
- ProSom (estazolam)
- Restoril (temazepam)
- Silenor (doxepin)
- Sonata (zelplon)

Carrier 5:55 PM Done Weekly

Sleep Aid Usage

- Lunesta (eszopiclone)
- ProSom (estazolam)
- Restoril (temazepam)
- Silenor (doxepin)
- Sonata (zelplon)
- Desyrel (trazodone)
- Belsomra (suvorexant)
- Antihistamines
- Melatonin
- Alcohol
- Other

Carrier 5:55 PM Done Weekly

In the last week...

Approximately how many alcoholic beverages did you consume?

- 0
- 1-2 drinks
- 3-6 drinks
- 7-12 drinks
- >12 drinks

Next

Tasks Surveys Settings Tasks Surveys Settings

Weekly travel questionnaire:

1. Did you travel across time zones this week?"

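### As displayed, the weekly sleep-aid list has no 'none used' answer, so within a submitted survey no use and an unanswered list cannot be told apart

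*Combined protocol and SAP*

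**What the plan says.** Use of sleep aids appears in four places.

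- **Objective (Study Design, 1.3.3.3, exploratory):** "Change in patient sleep aid usage in the control versus intervention arm".
- **Endpoint (3.3.3):** "Sleep aid utilization data will be collected via self-report in the app once a week".
- **Analysis (5.14.3):** "The total number of sleep aids being used by the patients, as well as the types, will be collected via weekly surveys". The section names no between-arm test or model and no rule for blank lists.
- **Instrument (Appendix C, Sleep aid usage survey):** the stem is "If you have used any sleep aids in the past week, select them from the list below". Two overlapping screen captures show 14 distinct choices: ten named prescription products, then antihistamines, melatonin, alcohol and a catch-all 'other'. No choice for no use is shown.

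The item displayed after it, "Approximately how many alcoholic beverages did you consume", has 0 as its first answer.

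Two general provisions could bear on blanks. Under 1.5.5, "study coordinators will track completion of surveys, and in the event of missing data will follow-up with subjects". Under 5.1, "Missing data will be imputed using the last collected data from the subject prior to dropout".

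**The concern.** Because the stem is conditional, a participant who used nothing answers correctly by ticking nothing. A participant who used something but passed over the list also ticks nothing. Unless the survey records something the documents do not describe, these two weeks look identical.

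The analyst then has two readings of a blank, and neither recovers the truth. Zero absorbs item non-response into no use. Missing removes every genuine non-user. At stake is the exploratory comparison of sleep-aid use. Its level could be under-counted, its arm contrast distorted if users in one arm skip the list more often, and its time course could show a false fall if skipping grows over the 12 weeks. The primary and secondary endpoints are not touched.

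**Working it through.** **Plan's own figure.** There is none for this endpoint. The plan's only sample-size calculation is for PROMIS Fatigue. It reproduces: 64 per arm gives t-test power 0.801 at half a standard deviation, and 64 / 0.93 = 68.8, so 69 per arm. It is unaffected by this point.

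**Inputs, all assumed.** Let p be the true share of weeks in which a sleep aid was used, and s the share of those weeks in which the list is left unticked inside a submitted survey. The documents give neither. The ranges used are p = 30% to 50% and s = 5% to 20%.

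**Step 1: the blank share does not identify use.** The blank share is (1 − p) + p × s, that is, 1 − p(1 − s). A blank share of 71.5% fits all of these:
- p = 28.5% with s = 0;
- p = 30% with s = 5%, since 0.30 × 0.95 = 0.285;
- p = 35.6% with s = 20%, since 0.285 / 0.80 = 0.356.

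**Step 2: blanks read as zero.** Apparent use is p(1 − s). With the same true use in both arms:

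| True use | Skip, arm A | Skip, arm B | Apparent A | Apparent B | False difference |
|---|---|---|---|---|---|
| 30% | 5% | 5% | 28.5% | 28.5% | 0 |
| 30% | 5% | 10% | 28.5% | 27.0% | 1.5 points |
| 30% | 5% | 20% | 28.5% | 24.0% | 4.5 points |
| 50% | 5% | 5% | 47.5% | 47.5% | 0 |
| 50% | 5% | 10% | 47.5% | 45.0% | 2.5 points |
| 50% | 5% | 20% | 47.5% | 40.0% | 7.5 points |

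A false difference needs unequal skipping. If skipping is equal but true use differs, the real difference shrinks by the factor (1 − s). For example, 50% against 30% with s = 10% appears as 45% against 27%, which is 18 points in place of 20.

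**Step 3: change over time, blanks read as zero.** If skipping rises from 0 to 20% with true use constant, the apparent fall is p × 0.20: 0.30 × 0.20 = 6 points, and 0.50 × 0.20 = 10 points.

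**Step 4: blanks read as missing.** Only weeks with a tick remain, so apparent use is p(1− s) / [p(1 − s)] = 100% in both arms, whatever the truth. The comparison of any use disappears.

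**Limit of the model.** These figures concern any use in a week, whereas 5.14.3 names the number of aids. If skipping does not depend on how many aids were taken, the mean count under zero coding shrinks by the same (1 − s).

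**The case against.** The strongest answer is that much of this is covered or cannot be known from the documents.

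- **Completion tracking.** Coordinators follow up missing surveys (1.5.5), so a wholly missed week may well be identifiable and can be set to missing. This stands, and it narrows the problem to an unticked list inside a submitted survey. Such a list is a legitimate answer for a non-user and need not be flagged.
- **The alcohol item.** An answer there shows that the survey was opened and, if both items share one page, that the participant scrolled past the list. It does not show that the list was answered.
- **Carry-forward.** The rule in 5.1 is tied to dropout. It does not treat missing weeks as no use, and it does not address a blank item.
- **Screen captures.** Appendix C shows images read into text. A forced response, or a further choice below 'other', cannot be ruled out. This stands, and the point is therefore about the list as displayed. A forced response without a 'none' choice would leave a non-user with no truthful answer.
- **Differential skipping.** Appendix B embeds the surveys in both app versions, and nothing in the documents shows that one arm skips more. This stands. Unequal skipping is a possibility, not a finding.

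Two stronger readings are tempting. A reader might infer that blanks are stored or analysed as zero, so that non-response is counted as abstinence. The documents do not say so: no storage or coding rule appears, and 5.14.3 speaks only of collection. A reader might also infer that this form is the check on the sleep-aid provisions in 1.4.1.5 and 1.5.4. It cannot be. The displayed form records no dose, which is what 1.4.1.5 concerns, and 1.5.4 places no limit on use that could be checked. Those two sections do not agree with each other and must be reconciled, but that is a separate matter.

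**Conclusion.** The point holds in a limited form. As displayed, the list gives a non-user no way to say so, and the plan has no rule for blanks, so item non-response within a submitted survey cannot be separated from no use. Use can be under-counted if blanks are read as zero, and non-users are lost if blanks are read as missing.

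Under zero coding, the arm comparison is biased only if skipping or true use differs between arms: unequal skipping can create a false difference, and equal skipping shrinks a real one. A false decline needs skipping that rises over time. Under the assumed rates the false arm difference is 1.5 to 7.5 points and the false decline 6 to 10 points. These are illustrations, not estimates for this trial. The endpoint is exploratory, so the impact is low; the case for acting is that the remedy is cheap.

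**What to change.** 1. Add a choice such as 'I did not use any sleep aid this week' to the list, and require at least one selection before the participant can continue. A forced selection should not be introduced without the new choice.
2. State in 5.14.3 that, from that change on, a week without a selection or without a submitted survey is missing, not zero. Applied to the present form, the same rule would discard the non-users.
3. Report blank lists collected before the change as ambiguous, with a sensitivity analysis coding them once as zero and once as missing. Zero coding gives a floor for reported use. Missing coding leaves only weeks with a tick, so it informs the number and types of aids among reported users but not the share using any.

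The cost is one answer option in the app, a short addition to 5.14.3, and one extra tap per week for participants. Blanks already collected cannot be resolved from the list itself.
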